the estimated frequencies, coupled with the low numbers in the control condition we chose to round any fraction for abstinence upward. This had the effect of producing a slightly higher effect in the control condition (n = 3 versus n = 2 abstinent) therefore rendering the simulated effect size more conservative). A fundamental difficulty is that the Frequentist approach cannot provide any indication regarding the relative probability of different values within the 95% Confidence Interval being the true parameter. The Bayesian estimate of the relative risk is slightly different (rounding was necessary in estimating the Frequentist but not the Bayesian solution), RR = 2.73, (95% CI: 0.90-11.44), however since these estimates are based on a posterior distribution it is possible to discuss the probability that an effect of a given magnitude is the governing parameter. Defining benefit as any RR > 1, the simulated posterior distribution shows that there is a 96% chance that the intervention confers this benefit and a more stringent definition (Relative Risk ≥ 1.50) is associated with an 85% probability that intervention confers

benefit. We stipulate that an intervention effect that has at least a 75% probability of increasing the relative risk of abstinence by >1.25 will warrant further investigation in a larger trial. While the above simulation provides a straight-forward example of how Bayesian modeling works, it is often necessary to use more sophisticated Bayesian approaches (e.g., logistic regression with Monte Carlo Markov Chain estimation methods). As such, final analyses will utilize Bayesian generalized linear modeling with multilevel-modeling for repeated measures data.

Bayesian Modeling Strategy Initial analyses examining group differences for baseline variables will use cross-tabulation, ANOVA's, and examination of correlations between baseline variables and specified outcomes. For the purposes of evaluating the comparability of groups, a posterior probability of $\geq 95\%$ will constitute evidence for statistically reliable differences. Baseline or demographic variables on which group differences are detected, and which are correlated with outcomes, meet the definition of confounders^{136, 137} and will result in two sets of analyses: one in which the relevant variable is included as a covariate and one in which it is not. This will permit determination of the degree to which any group differences might confound conclusions regarding treatment.

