
Broadly, the data analytic strategy will use generalized linear and multilevel models (SAS 9.4, R v. 3.5, and Stan 2.17) for both discrete (e.g. smoking abstinence) and continuous (e.g. depression) outcomes.¹³⁸⁻¹⁴⁰ Cross-sectional continuous (depression), dichotomous (smoking abstinence) and time-to-event (retention) data will be evaluated using generalized linear modeling or proportional hazards regression. All analyses will apply intention-to-treat principles with missing imputed as non-abstinent for smoking outcomes. For outcomes other than smoking, Bayesian approaches will implement joint modeling of observed outcomes and the missing data which is robust to ignorable missingness (i.e., MCAR and MAR).¹⁴¹ Sensitivity analyses will evaluate robustness of analytic conclusions to missing data. Non-ignorable missing data patterns will be addressed through pattern-mixture modeling methods.¹⁴² Convergence of Bayesian analyses on the posterior distributions via Monte-Carlo Markov chain (MCMC) will be assessed via graphical (Trace Plot, Autocorrelation Plot) and quantitative (Gelman-Rubin Diagnostics and Effective Sample Size) evidence. Evaluation of posterior distributions will permit statements regarding the probability that effects of varying magnitudes exist, given the data. Specification of diffuse, neutral priors will reflect the initial uncertainty regarding effect sizes. For all generalized linear models, priors for regression coefficients will be specified as \sim Normal ($\mu=0$, $\sigma^2=1 \times 10^4$), level one error variances will be specified as \sim Half-Normal ($\mu=0$, $\sigma^2=1 \times 10^4$). Choice of prior distribution for level two variances will follow Gelman's recommendations.¹⁴³ Bayesian Structural Equation Modeling (**BSEM**) prior specification will adapt recommendations from Muthén and Asparouhov.¹⁴⁴ Priors for the comparison of proportions will be specified as \sim Beta ($\alpha=1.0$, $\beta=1.0$).

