Conduct a preliminary randomized trial with depressed pregnant smokers comparing the BA to HW to evaluate the following: 1) The effect of BA on abstinence at 4 ½ months postpartum, which is a primary outcome. Logistic modeling will evaluate smoking abstinence, measured by biochemically verified TLFB, at 4 ½ months postpartum as a function of treatment group. **2) The effect of BA on depression at 4 ½ months postpartum, which is a primary outcome.** Generalized linear modeling will evaluate depression, measured by the PHQ-9, at 4 ½ months postpartum as a function of treatment group. **3) Feasibility of depressed pregnant smokers' acceptance of the smartphone delivery of BA and HW, and assessment components indicated by a) retention, which is a primary outcome, b) completion of prenatal and postpartum sessions, which is a primary outcome c) completion of study assessments, which is a secondary outcome d) strength of therapeutic alliance from both the participant and therapist perspective, which is a secondary outcome and e) participant and therapist ratings on satisfaction questionnaire, which is a secondary outcome.** Survival analysis will evaluate retention by modeling time to drop-out as a function of treatment condition. Binomial logistic modeling will evaluate the proportion of completed sessions as a function of treatment condition across the entire study as well as in the pre-natal and post-partum periods separately. Generalized linear models will evaluate participant and clinician measures of therapeutic alliance, measured by the WAI, as a function of treatment group. Similarly, generalized linear modeling will evaluate satisfaction as a function of treatment group. **4) Feasibility of study procedures as indicated by a) percentage of sessions interrupted by technical difficulties, which is a secondary outcome, and b) percentage of urine tests (cotinine and/or anabasine) received for biochemical verification of self-reported abstinence at 4 ½ months postpartum follow-up, which is a secondary outcome.** Binomial logistic models will evaluate the proportion of sessions interrupted for technical difficulties and the proportion of biochemically verified abstinence measures as a function of treatment. These analyses will provide estimates with 95% credible intervals for each of these proportions in each group that will permit assessment of feasibility.

Specific Analyses: Secondary Aim 1 (Stage IB)

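### As written, the primary PHQ-9 analysis conditions on treatment arm only, so the stated robustness to MAR does not cover drop-out that follows on-study mood

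*Combined protocol and SAP*

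**What the plan says.** Depression at 4½ months postpartum is a primary outcome of Aim 4. Its analysis is one sentence in Specific Data Analyses: Aim 4: "Generalized linear modeling will evaluate depression, measured by the PHQ-9", at 4½ months, with treatment group as the only predictor. No baseline or on-study PHQ-9 term is named.

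The Bayesian Modeling Strategy puts depression in the same class: "Cross-sectional continuous (depression), dichotomous (smoking abstinence) and time-to-event (retention) data will be evaluated using generalized linear modeling or proportional hazards regression". For outcomes other than smoking it then states that "Bayesian approaches will implement joint modeling of observed outcomes and the missing data which is robust to ignorable missingness", and names MCAR and MAR. The variables in that joint model are not listed. It adds that "Sensitivity analyses will evaluate robustness of analytic conclusions to missing data" and assigns pattern-mixture models to non-ignorable missingness, with no detail on either.

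Two general statements point toward longitudinal modelling. The Simulated Example closes with "final analyses will utilize Bayesian generalized linear modeling with multilevel-modeling for repeated measures data". The Bayesian Modeling Strategy also names generalized linear and multilevel models for discrete and continuous outcomes, with depression as its example of a continuous one.

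Table 2 (Aim 4) schedules the PHQ-9 at V0, PN1 to PN10, PP1 to PP4 and follow-up. Benchmarks for Establishing Feasibility and Acceptability sets the retention target at 70% or above.

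**The concern.** A model with one outcome per woman and arm as its only predictor has nothing but arm from which to predict a missing 4½-month score. Recent mood is a plausible driver of drop-out in depressed women, and the plan measures it at every session, yet the named model does not use it. The report could then claim protection against MAR drop-out that the analysis did not provide.

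Arm-dependent drop-out is also plausible. The health and wellness (HW) control has affective content removed and bars solution-focused work, so distressed women may leave the two arms for different reasons. Aim 4 Approach (Stage IB) says the data are to supply effect sizes for planning fully powered trials, so a distorted PHQ-9 difference would carry forward.

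**Working it through.** **The plan's own figures.** The documents give no SD, effect size or power for the PHQ-9. The only design calculation is the abstinence example, and it reproduces: P(RR>1) 96.2% against the stated 96%, and P(RR≥1.5) 84.9% against 85%. It says nothing about depression.

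**Step 1: what joint modelling does with arm only.** The unobserved scores integrate out: p(y_obs | θ) = ∫ p(y_obs, y_mis | θ) dy_mis. With one score per woman, independent given arm, this is the likelihood of the completers. The posterior is the complete-case posterior, valid only if staying is unrelated to the outcome within arm.

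**Step 2: size of the bias.** Assumptions, none from the documents: PHQ-9 SD 6; correlation r between the last on-study score and the 4½-month score of 0.5 to 0.7; staying is logistic in the last on-study score, slope 1 per SD (sicker women leave). Let E be the mean standardised last score among stayers, relative to the arm's own mean. The observed 4½-month mean is then off by r × SD × E, and

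bias of (BA − HW) = r × SD × (E_BA − E_HW).

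Negative values favour BA. Numerical integration gives E = −0.253 at 70% retention and −0.173 at 80%.

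- One arm mood-driven, other arm random, 30% loss: 0.5 × 6 × 0.253 = 0.76 to 0.7 × 6 × 0.253 = 1.06.
- The same at 20% loss: 0.5 × 6 × 0.173 = 0.52 to 0.7 × 6 × 0.173 = 0.73.
- Direction: if HW is the mood-driven arm, the bias is toward no effect; if BA is, it exaggerates benefit.
- Common mechanism, no effect: E_BA = E_HW, so zero.
- Common mechanism, 3-point benefit: BA retains 74% (E = −0.222) and HW 65% (E = −0.292). At r = 0.6, 0.6 × 6 × 0.070 = 0.25 toward no effect. It stays under 0.5 for slopes of 0.5 to 1.5.
- Same slope, no effect, retention 60% BA (E = −0.331) and 81% HW (E = −0.168): 0.6 × 6 × (−0.163) = −0.59, in favour of BA.

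**Step 3: simulation at N=50, r = 0.6, about 70% average retention.** The last column conditions, within arm, on baseline and last on-study PHQ-9 (assumed baseline correlations 0.35 to 0.40). It was run with 8,000 trials per row.

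| Scenario | Bias, plan's model | SD | 95% coverage | Bias (SD) using on-study score |
|---|---|---|---|---|
| Common mechanism, no effect | 0.00 | 2.02 | 94.7% | 0.00 (2.05) |
| Common mechanism, 3-point effect | +0.25 | 2.03 | 94.5% | 0.01 (2.07) |
| BA only mood-driven, 3-point effect | −0.84 | 2.01 | 93.1% | 0.00 (1.98) |
| BA only mood-driven, no effect | −0.91 | 2.03 | 92.8% | 0.00 (2.01) |
| Retention 60% BA, 81% HW, no effect | −0.58 | 2.03 | 94.1% | 0.00 (2.08) |
| Opposite mechanisms, no effect | −1.85 | 2.00 | 85.3% | −0.01 (2.05) |

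At N=60, which the statistical section gives in place of 50, the biases are the same to within 0.03 and the SD is about 1.85.

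**Step 4: is baseline adjustment enough?** With a 3-point effect, 30% loss and only BA mood-driven, adding baseline PHQ-9 moves the bias from −0.70 to −0.52 at r = 0.5, and from −0.97 to −0.79 at r = 0.7. That removes 26% and 19%.

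**The case against.** The strongest reply is that the plan does not exclude the earlier scores. It names multilevel models with depression as an example, and its joint model of observed outcomes is not limited to the 4½-month score. It also plans sensitivity and pattern-mixture analyses. This stands in part. A reader might infer that the plan rules out on-study PHQ-9 scores, and the documents do not support that. But the sentence that defines the primary contrast names treatment group only, and the outcome is labelled cross-sectional. Where longitudinal modelling is intended, as for the mediators in Secondary Aim 1, the plan says so. Unspecified sensitivity analyses, and models meant for non-ignorable missingness, do not make the primary analysis valid under ordinary MAR.

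A reader might also infer that the estimate is biased whenever drop-out follows mood, or always toward no effect. Neither holds: a common mechanism gives little or no bias, and the direction depends on which arm is affected. The 70% figure is a feasibility benchmark, not a forecast of loss.

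The consequences are limited too. Interval coverage stays near nominal except under opposite mechanisms. The only efficacy rule for going forward concerns the relative risk of abstinence, not the PHQ-9.

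Finally, a longitudinal model can do harm if its time form is wrong. In a simplified check (N=50, SD 6, about 30% missing, assumed trajectories, compound symmetry), a linear arm-by-time model biased the 4½-month contrast by about 1.1 points when the effect plateaued at PN10. The bias was about 3.3 points when the effect peaked and faded. Categorical time kept it within about 0.3. This stands, and it shapes the fix.

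**Conclusion.** The point holds as a mismatch between the analysis named for a primary outcome and the missing-data property claimed for it. Run as written, the PHQ-9 contrast is MAR-valid only given arm. A one-arm, mood-driven mechanism would shift it by about 0.5 to 1.1 points at 20 to 30% loss. Opposite mechanisms would shift it by about 1.1 to 2.1 points, and a common mechanism by less than 0.5 point. All sizes rest on the assumed SD, correlations, slopes and 3-point effect.

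Against a sampling SD of about 2 points, one trial's interval would usually still cover the truth. The bias does not shrink with sample size, however, and the estimate is meant for planning. The plan should be changed, because the remedy uses data already scheduled. The gain is in bias, not precision: under mood-driven drop-out the two approaches have about the same SD.

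**What to change.** In the Bayesian Modeling Strategy and in Specific Data Analyses: Aim 4, define the primary depression estimate as the BA − HW difference at 4½ months from a model that uses the on-study PHQ-9 scores. Either form would serve:

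- a multilevel repeated-measures model with categorical time, or a few prespecified time windows rather than a linear trend across birth and the break after it. It needs arm-by-time, a parsimonious prespecified covariance, and baseline PHQ-9 as a covariate or a response, not both;
- Bayesian imputation of the 4½-month score from arm, baseline PHQ-9 and the latest on-study PHQ-9. This is closest to the estimator checked above.

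Keep the cross-sectional model as a sensitivity analysis, and attach the MAR statement only to the longitudinal or imputation model.

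The cost is wording and some analyst time, with no new visits or data. The real burden is fixing the time and covariance form in advance, since up to 16 scheduled scores per woman (1 + 10 + 4 + 1) at N=50 will not support a rich covariance structure.

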Simulated Example: As an example of applying a Bayesian analysis, the Figure below depicts the prior and posterior distributions for the probability, and the posterior distribution of the relative risk of smoking abstinence as a function of intervention based on simulated data. Panel A shows the prior and posterior distributions of the absolute probability of treatment initiation as a function of the intervention. The prior distributions (dashed lines) assume that for both intervention conditions all probabilities of smoking abstinence are equally likely (i.e., $\sim\text{Beta}[a=1, b=1]$). The posterior distributions (solid lines) reflect anticipated intervention effects:

1) N= 60 participants randomized in a 1:1 ratio, 2) 7.6% and 25% rates of abstinence at six months post-partum in the control and intervention conditions, respectively (i.e., $\sim\text{Beta}[a=3.28, b=28.72]$ and $\sim\text{Beta}[a=8.5, b=23.5]$ for control and intervention conditions, respectively). Panel B reflects the posterior distribution of the relative risk (calculated directly from the distributions in Panel A (i.e. $p(\text{Abstinence in Intervention})/p(\text{Abstinence in Control})$)) for smoking abstinence. From a Frequentist perspective, this would yield a Fisher Exact $p \leq 0.18$ and relative risk of 2.67 (95% CI 0.78-9.09). (Note: For the Frequentist calculations, to address the non-integer nature of

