Mediational modeling will examine the degree to which putative mechanisms of behavioral change transmit the effects of the intervention on the specified outcomes. BSEM will investigate mediation of treatment effects by hypothesized mechanisms (positive and negative affect and cognitive deficits) utilizing MPlus v. 8.0.¹⁴⁴⁻¹⁴⁶ Measurement of positive and negative affect will use the PANAS. Measurement of cognitive deficits will use the CF-A. Models will evaluate whether change over time (captured using growth factors) in positive affect, negative affect and cognitive deficits, measured with the PANAS and CF-A, mediates the effect of treatment at six months post-partum. Examination of the posterior distribution of the indirect effects will evaluate the probability that mediational effects exist. For model simplicity it may be necessary to break these analyses into two distinct mediation models. However MCMC estimation has demonstrated superior small sample performance relative to maximum likelihood-based approaches in continuous, normally distributed data.^{147, 148} As discussed in the **Specific Data Analytic** section, minimal variability in growth factors representing change over

time, which may be partially a function of small sample size will result in use of an alternative approach.

Specific Data Analyses: Aim 4

The specific quantitative, analytic plan will focus on Primary Aim 4 and Secondary Aim 1.

Primary Aims

Aim 4 (Stage IB)

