Evaluate change in hypothesized treatment mechanisms including positive affect, negative affect and cognitive impairment in relation to treatment effects on smoking and depression. It would be ideal to evaluate the change in positive affect, negative affect and cognitive impairment as mediators of treatment effects on 4 ½ month post-partum outcomes via structural equation modeling. Specifically, we could model the change over time in each mediator and evaluate the degree to which each growth factor might transmit the effect of treatment. However, it is possible that a sample size of N = 50 will not provide enough variability to estimate certain parameters implied by such a model (e.g. the slope of change in each of these mediators may have minimal variance and function poorly as a mediator). If this latter scenario obtains, we will evaluate each component of a mediational analysis in separate analyses to evaluate the evidence for mediation of treatment effects by positive affect, negative affect and cognitive impairment. Specifically we will: a) evaluate the change over time in each mediator as a function of treatment using multi-level modeling; b) Evaluate the effect of

treatment on the outcome (smoking cessation or depression); and c) evaluate the outcome (smoking cessation or depression) as a function of change in the mediator captured either through a difference score (six months – baseline) or residual change score (six months residualized on baseline). While the former (SEM) approach would provide a more elegant test of the overall model of behavior change, the latter may be necessary based on the properties of the sample.

PARTICIPANT SAFETY MONITORING PLAN

Assessment of Worsening Depression, Anxiety and Suicide Risk

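### Step (c) of the fallback mediation analysis names no treatment term, so as written a BA effect on both mediator and outcome can pass for evidence of mediation

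*Combined protocol and SAP*

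**What the plan says.** The section on specific analyses for Secondary Aim 1 prefers a structural equation model in which growth factors for positive affect, negative affect and cognitive function carry the treatment effect. It then warns that "it is possible that a sample size of N = 50 will not provide enough variability" to estimate such a model. In that case, "we will evaluate each component of a mediational analysis in separate analyses to evaluate the evidence for mediation of treatment effects".

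The three components are:

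- (a) "evaluate the change over time in each mediator as a function of treatment using multi-level modeling";
- (b) the effect of treatment on the outcome;
- (c) "evaluate the outcome (smoking cessation or depression) as a function of change in the mediator captured either through a difference score", or through a residual change score.

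Treatment appears in (a) and (b). It does not appear in (c), and no other section adds it. Bayesian Modeling Strategy adds covariates only for baseline or demographic variables that differ between groups and correlate with outcome. The section on smoking cessation or depression treatment after enrollment adds outside treatment as a covariate where needed.

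For the structural equation model the plan says "Examination of the posterior distribution of the indirect effects will evaluate the probability that mediational effects exist". It gives no threshold for mediation and no rule for combining (a), (b) and (c).

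**The concern.** The trial's theoretical model holds that BA changes affect, cognition, depression and smoking. Treatment is then a common cause of mediator change and outcome. A regression of outcome on mediator change across both arms, without a treatment term, picks up the difference between arms as well as any relation within arms. An inert mediator acquires a non-zero coefficient because BA women have both more mediator change and better outcomes. Residualising the mediator on its own baseline does not help, because the arm difference in change remains.

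The artefact grows with BA's effect on the mediator and with its effect on the outcome by other routes. A positive step (a) therefore offers no protection: it is most likely to be positive when step (c) is most distorted. Secondary Aim 1 could credit a mechanism that the data do not support and carry it into the design of the next trial.

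**Working it through.** **Inputs from the documents.** Step (c) as quoted. N = 50 (Secondary Aim 1 analyses); the simulated example instead uses "N= 60 participants randomized in a 1:1 ratio". Abstinence: "7.6% and 25% rates of abstinence at six months post-partum in the control and intervention conditions". Diffuse priors, so posterior tail probabilities are close to one-sided p-values. Retention benchmark 70%: 0.70 × 50 = 35, run as 36 for equal arms.

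**Assumptions not in the documents.** Equal BA effects d (in SD units) on mediator change and outcome; no mediator effect within arms; no other confounding; evidence counted when the posterior probability in the expected direction is at least 95%. The plan's only 95% posterior rule, that such a probability "will constitute evidence for statistically reliable differences", concerns baseline comparability.

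**The plan's own figures.** The plan states no error rate for mediation. Its simulated abstinence example does reproduce. From Beta(8.5, 23.5) and Beta(3.28, 28.72), the relative risk has median 2.75 (0.90 to 11.47), P(RR > 1) is 96.2% and P(RR ≥ 1.5) is 84.9%. The plan gives 2.73 (0.90 to 11.44), 96% and 85%. Fisher's test on 8/30 versus 3/30 gives p = 0.181.

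**Size of the artefact.** Let M = dT + e and Y = βM + τT + u, with T coded 0/1 at 1:1 and unit error variances. The variance of T is 0.25, so the coefficient of Y on M without T is

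β + 0.25·τ·d / (1 + 0.25·d²).

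With T in the model it is β. For an inert mediator (β = 0, τ = d), the induced correlation is r = 0.25d²/(1 + 0.25d²):

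- d = 0.3: 0.0225/1.0225 = 0.022
- d = 0.5: 0.0625/1.0625 = 0.059
- d = 0.8: 0.16/1.16 = 0.138
- d = 1.0: 0.25/1.25 = 0.200

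**Hand check at N = 50.** The expected t is r√48/√(1 − r²), and the 95% quantile of t on 48 df is 1.677. At d = 1.0, t = 0.2 × 6.928/0.980 = 1.41, and P(Z > 1.677 − 1.414) is about 40%. At d = 0.5, t = 0.408, and P(Z > 1.269) is about 10%. The simulation agrees.

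**Simulated false support, continuous outcome, N = 50.**

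| d | (c), no treatment term | (c), with treatment | (a) and (c), no treatment term in (c) | (a) and (c), with treatment in (c) |
|---|---|---|---|---|
| 0 | 4.9% | 5.0% | 0.3% | 0.3% |
| 0.3 | 6.6% | 4.7% | 2.5% | 1.3% |
| 0.5 | 10.9% | 5.1% | 7.6% | 2.7% |
| 0.8 | 25.3% | 5.0% | 23.9% | 4.3% |
| 1.0 | 41.6% | 5.1% | 41.2% | 4.9% |

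Simulation error is a few tenths of a point (a repeat gave 41.3% at d = 1.0). Requiring (b) as well leaves 5.4%, 22.7% and 40.8% at 0.5, 0.8 and 1.0 SD.

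**Variants of (c) without treatment, at 0.5, 0.8 and 1.0 SD.**

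- N = 36: about 10%, 20 to 21% and 33%.
- N = 60: 11.5%, 28.7% and 46.8%.
- N = 50, two-sided 5%: 7.1%, 16.1% and 29.6%.

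**Abstinence.** Logistic models, 7.6% versus 25%, N = 50, 2,500 simulated trials per scenario, BA effect on the mediator of 0.5, 0.8 and 1.0 SD. One-sided: 12.1%, 15.1% and 20.3% without treatment; 6.0%, 5.2% and 5.9% with it. Two-sided without treatment: roughly 7 to 9%, 9 to 10% and 12%.

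**The case against.** The strongest reply is that this is a contingency within an exploratory analysis. Treatment Mechanisms describes the mediator analyses as exploratory. The fallback applies only if growth factors vary too little, and the plan calls that possible, not expected. The only rule for advancing to a larger trial concerns abstinence. All of this stands and limits the severity.

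The text also does not exclude covariates. Step (c) is silent, and an analyst might add treatment unprompted. That stands too, which is why the point is put as what the plan says as written. Still, treatment is named in (a) and (b), and an analyst following (c) literally would leave it out.

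Three stronger readings are tempting but unsupported:

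- A reader might infer that the fallback contradicts the plan's own criterion because it yields no posterior for the indirect effect. That criterion belongs to the structural equation model, and the same section announces an alternative approach if growth factors vary too little.
- A reader might infer that (c) loses women whom (b) keeps, because a change score needs an end value. The plan does not specify complete cases. It sets intention-to-treat for all analyses, joint modelling of missing data for non-smoking outcomes, and sensitivity analyses.
- A reader might want woman-specific slopes in place of the change score. Low slope variance is what triggers the fallback, and slopes from a model containing treatment shrink toward their arm means and become nearly collinear with it.

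**Conclusion.** The point holds for step (c) as written: with no treatment term, BA's effect by other routes is credited to the mediator, and requiring step (a) does not cure it. Its direction follows from the trial's own hypothesis; its size does not follow from the documents. A reader might take 11 to 41% as the plan's false-positive rate. It is not. The documents give no BA effect on the PANAS, CF-A or PHQ-9 and no decision rule for mediation. Those figures need effects of 0.5 to 1.0 SD on both variables, a continuous outcome and a one-sided 95% rule. At 0.3 SD the inflation is negligible, and for abstinence at the plan's illustrative rates it is at most about 20% over the range examined. The 5% comparison further assumes no other mediator-outcome confounding. This is a modest fault in a contingent secondary analysis, worth correcting because the correction is nearly free.

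**What to change.** Reword step (c) as: *outcome as a function of mediator change and treatment group*, keeping the difference score or residual change score. Optionally, report the posterior of the product of path a (treatment to mediator) and path b (mediator to outcome, given treatment), and state the scale for abstinence, where the logistic path is not linear.

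The cost is one clause in the plan and one model term, with no new data. The interval for the mediator coefficient widens slightly. With mediator variance 1 within arms and an arm difference of 0.5 SD, the variance inflation from adding treatment is 1 + 0.25 × 0.25 = 1.06; at 1.0 SD it is 1.25. The plan should also say that adjusting for treatment does not remove confounding of mediator and outcome by other variables, since mediator change is not randomised.

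The same sentence defines change from a six-month value, whereas the last scheduled assessment is at 4½ months postpartum. That is a separate matter, but it can be settled in the same edit.
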